6.4.7. Other Safety Outcomes

7. DATA MANAGEMENT

Data will be kept in locked filing cabinets in a locked room away from the clinical area. All data that is computer generated will password protected. The FDA, New York Presbyterian Hospital, the IRB, and the Office for Human Research Protection (OHRP) may have access to the study records without the patient's permission and will maintain confidentiality of the information.

8. DATA ANALYSIS AND STATISTICAL CONSIDERATIONS

8.1. Hypotheses

Subject who did not respond at a dose of 75mg daily, eltrombopag will respond with increasing platelet count to $> 50,000$ and $> 20,000$ above baseline at a higher daily dose of 100, 125 and 150mg.

8.2. Study Design Considerations

8.2.1. Sample Size Assumptions

The trial will have a 80% statistical power at the 5% level of significance (two sided) to detect a difference in the proportion of patient receiving increased dose of eltrombopag with a primary response (Platelet Count $\geq 50,000$ per cubic millimetre and $> 20,000$ above baseline) to patients without a primary response in the placebo group. assuming 50% of patients randomized to active drug will have a response and 5% of patients

randomized to placebo would have a response. An interim analysis will be performed after 18 subjects to test for futility and efficacy and also to re-estimate sample size. If neither futility nor efficacy are met the trial would continue to enroll. Based on the observed treatment effect at the interim analysis the sample size would be allowed to expand to up to 60 subjects

8.2.2. Sample Size Sensitivity / Re-estimation

If the estimates of study size are incorrect, a preliminary look will take place after 18 patients to see if the study size needs to be increased.

8.3. Data Analysis Considerations

8.3.1. Key Elements of Analysis Plan

The analysis would primarily be descriptive except for the primary endpoint. In order to make the study feasible, the current plan for 36 patients does not allow for much flexibility. It does allow for a confirmatory study from the patients on placebo who can then follow the 8 weeks of dose escalation treatment as an open label study (note they will have been on 75 mg of eltrombopag for at least 11 weeks at that time). All secondary analyses will be underpowered but will be descriptive.

Analysis of efficacy will be based on the intention to treat population of all subjects who underwent randomization.

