4. SUBJECT SELECTION AND WITHDRAWAL CRITERIA

4.1. Number of Subjects:

60 subjects will be enrolled.

4.2. Inclusion Criteria:

Subject or their parent/ guardian has signed and dated a written informed consent

Males and Females aged 3 year or older, who can swallow a tablet, and are diagnosed with chronic ITP according to the new consensus guidelines (Provan, Blood, 2009) are eligible.

No indication of a disease which may cause thrombocytopenia other than ITP---- no specific testing required

Subjects with thrombocytopenia $\leq 50,000 /uL$ after at least 21 days of daily dosage with eltrombopag 75mg

Stable dosage of concomitant treatments for ITP
 ≥ 2 weeks or longer (corticosteroids);

At least 2 weeks from rescue therapy for ITP (WinRho, IVIG, corticosteroids, platelet transfusion) or 1 week if therapy has clearly been ineffective

At least 4 weeks from rituximab treatment

Pregnant or Lactating Women are excluded

Women of child-bearing age with a negative pregnancy test within 7 days of enrollment and who agree to use acceptable methods of birth control will be eligible for this study

Female subjects or female partners of male subjects must either be of non-child bearing potential (hysterectomy, bilateral oophorectomy , bilateral tubal ligation or post menopausal for more than one year) OR, if of child bearing potential, using one of the following highly effective methods of contraception.
-complete abstinence from intercourse

- Intrauterine device (IUD)
- Two forms of barrier contraception. diaphragm plus spermicide, or for males condoms plus spermicide.
- Male partner is sterile and is the only partner of the female.
- Systemic contraceptives

4.3. Exclusion Criteria:

Previous history of eltrombopag-related LFT elevation that required sustained interruption of treatment

Previous history of immediate or delayed hypersensitivity reaction or idiosyncrasy to drugs chemically related to eltrombopag

Known HIV Infection

History of Arterial or Venous Thrombosis within the past year or requiring ongoing therapy

Known Active Hepatitis C infection

Elevated AST/ALT or Creatinine > 1.5 times upper limit of normal in 4 weeks prior to enrollment*

Abnormalities in WBC, ANC and Hemoglobin > 1.5 times upper or lower limit of normal*

* Subjects can be rescreened to be included

4.4. Withdrawal Criteria:

Subject may withdraw consent at any time

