5. STUDY TREATMENTS

5.1. Treatment Assignment

Subjects will be randomly allocated in a two to one ratio to receive treatment or placebo. Subjects and investigators will be blinded to randomization. Randomization will be stratified according to splenectomy status. Randomization will be performed at the time of informed consent with a computer generated randomization table

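### The current sample size reads as 36 in one section and 60 in another, no re-estimation decision connects them, and the 80% power, stated without an N or a test, fits 36 and not 60

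*Combined protocol and SAP*

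**What the plan says.** All references are to the combined protocol and SAP.

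- **Section 4.1 (Number of Subjects)**, without condition: "60 subjects will be enrolled".
- **Section 8.3.1 (Key Elements of Analysis Plan)**: "the current plan for 36 patients does not allow for much flexibility".
- **Section 8.2.1 (Sample Size Assumptions)**: "The trial will have a 80% statistical power" at the two-sided 5% level, "assuming 50% of patients randomized to active drug will have a response and 5% of patients" on placebo. No N and no test are attached. Section 3.1 repeats the statement, again with neither.
- **Section 8.2.1** also plans a look after 18 subjects for futility, efficacy and sample size re-estimation. Depending on the observed effect, "the sample size would be allowed to expand to up to 60 subjects". Section 8.2.2 repeats the re-estimation purpose.
- **Section 5.1**: "Subjects will be randomly allocated in a two to one ratio to receive treatment or placebo".
- **Section 8.3.1.1** names logistic regression for binary response and reports the look at 18. The results given are trends by splenectomy status and sex, and removals for SAEs. Further analyses are planned at 36 and 60 patients. The interim paragraph of section 6.4.6.2 reports the same results.

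**The concern.** The primary endpoint is the only analysis that section 8.3.1 does not call descriptive, so its sample size and power are the design figures that matter most. Two current passages give different sizes. The power statement cannot settle which one is meant, because it names no N. Nor can the interim report, because it gives no response rates by arm, no re-estimated N and no decision.

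A reader therefore cannot tell whether 60 is the final target or still a ceiling, whether the 50% versus 5% assumption survived the interim look, or what effect the final trial is sized to detect. The section also mixes time frames: section 8.2.1 describes the look at 18 as still to come, while section 3.1 says it has been performed.

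**Working it through.** **Inputs from the documents.** Active rate p_A = 0.50 and placebo rate p_P = 0.05 (8.2.1); two-sided alpha 0.05 (8.2.1); allocation 2:1 (5.1). So 36 means 24 + 12 and 60 means 40 + 20. The test is not stated, so several were tried. All powers are for a single look with no dropout unless noted.

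**Step 1: recover the N behind 80%.** The pooled normal formula for the placebo group, with ratio k = 2, is

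n_P = [z₀.₉₇₅ √((1 + 1/k) p̄(1 − p̄)) + z₀.₈₀ √(p_A(1 − p_A)/k + p_P(1 − p_P))]² / (p_A − p_P)²

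- p̄ = (2 × 0.50 + 0.05)/3 = 0.35
- first term: 1.960 × √(1.5 × 0.35 × 0.65) = 1.145
- second term: 0.842 × √(0.125 + 0.0475) = 0.350
- n_P = (1.145 + 0.350)² / 0.45² = 11.03, rounded up to 12

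The total is 3 × 12 = **36**.

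**Step 2: exact power at both sizes.** Power is the sum, over all response counts a (active) and c (placebo), of Bin(a; n_A, 0.50) × Bin(c; n_P, 0.05), counting the tables that the test rejects.

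| Test | N = 36 (24:12) | N = 60 (40:20) |
|---|---|---|
| Fisher's exact | 81.5% | 97.6% |
| Likelihood-ratio (logistic model, arm only) | 91.5% | 98.8% |
| Uncorrected chi-square | 86.7% | 98.6% |
| Yates chi-square | 72.6% | 96.0% |

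Fisher power at N = 33 (22:11) is 74.6%, so 36 is the smallest 2:1 size among those checked that reaches 80% with that test. The stated 80% is reproduced at 36. It is not reproduced at 60 by any test in the table.

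**Step 3: can other assumptions bring 60 down to 80%?** With Fisher's test at N = 60, power is 95.8% at alpha 0.025 and 91.4% at alpha 0.0167. If dropouts count as non-responders at alpha 0.05, an assumed 10% dropout gives 95.2% and 20% gives 91.3%. None of these comes near 80%.

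**Step 4: what effect does 80% at 60 imply?** Holding placebo at 5%, Fisher power at 40:20 is 77.9% for an active rate of 35%, 80.2% for 36% and 87.8% for 40%. So 80% at N = 60 corresponds to about **36% versus 5%**.

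**Step 5: zero cells.** The probability of no placebo responder is 0.95¹² = 54% at N = 36 and 0.95²⁰ = 36% at N = 60. In those tables the ordinary logistic estimate is infinite and its Wald test is not usable. The choice of test therefore matters at both sizes.

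**Step 6: is the route from 36 to 60 documented?** Section 8.2.1 permits it. Sections 6.4.6.2 and 8.3.1.1 report the look that would have triggered it, without an N or a decision. Section 4.1 states the end point of the route and section 8.3.1 its starting point, each as current.

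**The case against.** **The two numbers are linked.** The natural reading is a design of 36 with a re-estimation ceiling of 60, and leftover wording in 8.3.1. This stands as an explanation of where the numbers came from. It does not reconcile them: a permitted maximum that depends on the observed effect is not the same as an unconditional 60, and the step between them is not reported.

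**The plan never claims 80% at 60.** This also stands. A reader might infer that the stated power is simply wrong. But 80% at the starting size under the starting assumptions is a correct statement, and 36 reproduces it. If the sample grew because the observed effect was smaller, 50% versus 5% is no longer the relevant calculation at 60. The defect is that the statement is not tied to an N.

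**More power does no harm.** A reader might infer from the inconsistency that the trial is underpowered. Under the stated rates 60 errs in the safe direction, so the documents do not support that.

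**Logistic regression is the named method, and its power looks poor.** An ordinary Wald test gives 29% at 36 and 62% at 60, but only if every table with an empty cell is counted as a non-rejection. Section 8.3.1.1 does not specify a Wald test. From the same arm-only model the likelihood-ratio test gives 91.5% and 98.8%, and a Wald test after adding 0.5 to each cell gives 68.7% and 97.2%. The low figures are therefore not what the plan implies. What remains is the need to name a test that copes with zero cells.

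**Fisher's test is an inference.** True: no section names it. The match to 36 does not rest on it, since the pooled formula returns the same number.

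**Conclusion.** The point holds as a documentation and sizing defect that should be corrected. Sections 4.1 and 8.3.1 give different current sizes (60 and 36), and the re-estimation decision that could connect them is not reported. The 80% power carries no N or test. It fits 36 and is not the power at 60, which is about 98% under the same rates. Read as 80% power at 60, it would mean about 36% versus 5% with Fisher's test.

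The inconsistency itself is certain from the text. The power figures rest on 2:1 allocation, the stated rates, a single look and no dropout. The plan states no alpha adjustment for its looks, and any adjustment would lower them. Nothing here shows that the trial is too small or that the power claim was false for the size it was made for.

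**What to change.** 1. State one current N in 4.1, 8.2.1 and 8.3.1, and remove the reference to a plan for 36 if 60 is final.
2. In 8.2.1, report the re-estimation decision taken after the look at 18: the resulting N, its basis, and any revised response rates. If the decision was not to revise the rates, say so and give the reason for the N chosen.
3. Restate the power in 3.1 and 8.2.1 for that N, with the rates, the split by arm, the final alpha after allowing for interim looks, and the test.
4. Make that test the one used for the primary analysis in 8.3.1.1. Since a placebo arm with no responders is likely enough to plan for (54% at 36, 36% at 60), choose an exact or likelihood-ratio test and not an ordinary Wald test. If the likelihood-ratio test is chosen, say whether its p-value is exact or from the chi-square approximation.

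The cost is text changes only, with no extra patients.

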8.3.1.1. Interim analysis

Results of Interim analysis:

In the interim analysis of 18 subjects, the data suggests that non-splenectomized patients tended to have greater average platelet counts compared to splenectomized patients for the first 8 weeks in the open-label extension phase. When subjects were on active drug, the results revealed that males tended to have a higher complete response rate compared to females.

Of note, three subjects were removed due to SAEs, however only one patient was removed because of a study drug related event (elevated LFTs). Further analysis will be performed after 36 patients and 60 patients are enrolled to evaluate the long term efficacy and safety of eltrombopag at doses higher than 75 mg.

Primary Response Criteria:

Complete Response (CR) will be defined as a 2 consecutive platelet counts $\geq 50,000 / \mu\text{L}$ AND $> 20,000$ more than the baseline platelet count at enrollment within the 8 week increased dose window not as a result of rescue treatment. Partial Response (PR) will be defined as a 2 consecutive platelet counts $\geq 50,000 / \mu\text{L}$ OR $> 20,000$ more than the baseline platelet count at enrollment within the 8 week increased dose window not as a result of rescue treatment. Odds of response will be analyzed using logistical regression for binary response variables.

Secondary Response Criteria:

- Platelet Count \geq 50,000 and $>$ 20,000 above baseline for at least 3 of the last 4 of 8 weeks independent of rescue therapy
- Platelet Count \geq 50,000 /uL and $>$ 20,000 above baseline for any 4 of 8 weeks independent of rescue therapy
- At least One Platelet count \geq 100,000
- Number of weeks with Platelet Counts \geq 50,000 /uL and $>$ 20 from baseline in 8 Weeks reduction of bleeding score from baseline to the last count of the study improvement of HRQoL
- Number of weeks with Platelet Counts $>$ 100,000 in 8 Weeks

Secondary Efficacy Endpoints:

- Dose required achieving first platelet count \geq 50,000 /uL ?and $>$ 20 from baseline
- Average Platelet Count at each dose level
- Bleeding scores using Page score and WHO score
- Use of Rescue Treatment

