1. INTRODUCTION

1.1. Background

In previous clinical studies of eltrombopag in ITP, there are some patients who have been reported as non-responders at the maximal approved dose of 75mg daily. The trend in both normal volunteers (Jenkins et al Blood 2007) and in patients with ITP suggests an increasing response rate with increasing doses of eltrombopag up to a dose of 75 mg . ([name] et al. NEJM 2007) In fact, at 50 mg there was a 70% response rate and at 75 mg there was an 81% response rate in the initial ITP study.([name] et al. NEJM 2007) Furthermore, the occurrence of platelet counts $> 200,000/\mu\text{l}$ was substantially more frequent at 75 mg compared to 50 mg as well. In the confirmatory study, approximately 1/3 of the patients who did not respond to 50 mg did subsequently respond to 75 mg, although the response rate overall was only 59% compared to 16% in placebo.([name] et al. Lancet 2009). In the RAISE study, two key issues emerged. First the majority of patients ended up on 75 mg by the end of the study. Second, the odds of responding at each assessment point was barely 50% if not very occasionally below 50% during the study. (Cheng et al. Lancet 2011) Altogether these data suggest to us that a higher dose of eltrombopag may be useful in some patients

Data from the PETIT and PETIT2 studies in pediatric patients (who seem to metabolize eltrombopag differently especially at younger ages) found that in the middle and lowest age cohorts, even doses of 75 mg were sometimes insufficient to obtain a response. This was confirmed in the youngest cohort who thus far have required doses $> 2 \text{ mg/kg}$ in almost all cases (and even $> 3 \text{ mg/kg}$) in order for the children to respond. In the middle cohort this was dose limiting because a ceiling of 75 mg was reached rapidly if the child weighed more than 37.5 kg. ([name] et al, PETIT in press Lancet Haem 2015)

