2. OBJECTIVE(S)

2.1. Primary Objective

To determine the proportion of patients with chronic ITP who do not respond to 75 mg of eltrombopag daily given for at least 3 weeks but then do respond to eltrombopag given daily first for 2 weeks at doses of 100, then for 2 weeks at 125 mg and finally for 4 weeks at a dose of 150mg daily. The intial double-blind phase will stop if/when the platelet count exceeds 100,000/uL. Complete response (CR) will be defined as 2 consecutive platelet counts of greater than or equal to 50,000 AND an increase of greater than or equal to 20,000 from the study baseline within the 8 week increased dose window not as a result of rescue treatment. Partial response (PR) will be defined as 2 consecutive platelet counts of greater than or equal to 50,000 OR an increase of greater than or equal to 20,000 from the study baseline within the 8 week increased dose window not as a result of rescue treatment.

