The trial will have an 80% statistical power at the 5% level of significance (two sided) to detect a difference in the proportion of subjects receiving increased dose of eltrombopag with a primary response (2 consecutive platelet counts of > 50,000 and an increase of > 20,000 from the study baseline with in the 8 week increased dose window not as a result of rescue treatment) to subjects without a primary response in the placebo group assuming 50% of subjects randomized to active drug will have a response and 5% of subjects randomized to placebo would have a response. The same statistical test will be run for subjects who achieve partial response. An interim analysis was performed after 18 subjects to test for futility and efficacy.

Dose modification during the long term extension portion of the trial will be made on the basis of individual platelet response to a maximal dose of 150mg. All subjects can be monitored at 4 weeks intervals and then can go to every 8 weeks for the remainder of the study at the discretion of the investigator (investigator may require subjects to come in for additional monitoring if deemed necessary).

If the platelet count is > 150,000 ul and < 400,000 ul the daily dose will be adjusted and if > 400,000 ul the medication will be held and monitor will be as per the prescribing information for eltrombopag in the package insert. However, if the P-I determines that adjusting the subject's dose will negatively affect the subject, he or

she may decide not to escalate or reduce the subject's dose. Circumstances in which this may occur include, but are not limited to: investigator is tapering other medications or the subject has a viral infection. Viral infections have been known to both increase and decrease platelet count in patients with ITP. It is suggested that the increased presence of inflammatory molecules during a viral infection increases platelet production, causing platelet count to increase. Alternatively, platelet count may decrease by virtue of activating the reticuloendothelial system causing greater phagocytosis of antibody-coated platelets and/or platelet production.

Laboratory/Assessment Testing

Please see Appendix 1 for Schedule of Events.

Screening

CBC with Differential
Reticulocyte Count
Peripheral Smear
CMP (Sodium, Potassium, Bicarbonate, Chloride, BUN, Creatinine, Glucose, Calcium, Total Protein, Albumin, including AST/ALT, Fractionated Bilirubin Level)
Urine Pregnancy Test (when appropriate)

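### Logistic regression, the only method named for the primary response, has no stated test, model terms or rule for an arm without responders; at the plan's 5% placebo rate an empty placebo arm occurs in 36% of trials at N=60 and 54% at N=36

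*Combined protocol and SAP*

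**What the plan says.** Section 8.3.1 makes the primary endpoint the only analysis that is not descriptive, in the intention-to-treat population. The only inferential method named for it is one sentence under Primary Response Criteria in 8.3.1.1: "Odds of response will be analyzed using logistical regression for binary response variables". The sentence follows the definitions of both complete response (CR) and partial response (PR).

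Elsewhere the aim is put in terms of proportions. Section 2.1 begins "To determine the proportion of patients with chronic ITP who do not respond to 75 mg of eltrombopag daily", and 8.2.1 powers the trial for "a difference in the proportion of patient receiving increased dose of eltrombopag with a primary response", "assuming 50% of patients randomized to active drug will have a response and 5% of patients" on placebo. No method is given for that difference. Section 3.1 adds "The same statistical test will be run for subjects who achieve partial response" without naming the test.

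Allocation is 2:1, stratified by splenectomy status (5.1). Section 4.1 states "60 subjects will be enrolled"; 8.2.1 treats 60 as the ceiling after re-estimation, and 8.3.1 still speaks of a plan for 36. Section 3.1 also records that "An interim analysis was performed after 18 subjects to test for futility and efficacy", and that each subject is unblinded after Part 1.

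**The concern.** With a 5% placebo rate and a small placebo arm, the plan expects about one placebo responder or fewer: 20 × 0.05 = 1.0 at N=60 and 12 × 0.05 = 0.6 at N=36. An arm with none is therefore an ordinary outcome. In that table the maximum-likelihood odds ratio is infinite, and the Wald interval and p-value carry no information, although the data may strongly favour the higher dose.

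The plan does not say what happens then. If the test is chosen after the empty arm has been seen, the trial's single inferential result depends on a decision made with knowledge of the data.

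**Working it through.** **Inputs.** 50% vs 5%, two-sided 5%, 80% power (8.2.1); 2:1 allocation (5.1); N=60 (4.1) and N=36 (8.3.1). With an exact 2:1 split the arms are 40:20 and 24:12.

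**1. The plan's own figure.** Pooled two-proportion formula, with mean rate (0.05 + 2 × 0.50)/3 = 0.35:

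n(placebo) = [1.96 √(1.5 × 0.35 × 0.65) + 0.8416 √(0.05 × 0.95 + 0.50 × 0.50/2)]² / 0.45² = (1.145 + 0.350)² / 0.2025 ≈ 11.0, just above 11, so 12.

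That gives 12 placebo + 24 active = 36, matching 8.3.1. The 80% reproduces for a comparison of two proportions; Fisher's test at 24:12 has 81.5%.

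**2. Chance of no placebo responder**, (1 − p)^n:

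| Placebo rate | N=60 (n=20) | N=36 (n=12) |
|---|---|---|
| 2% | 66.8% | 78.5% |
| 5% (plan) | 35.8% | 54.0% |
| 10% | 12.2% | 28.2% |
| 16% | 3.1% | 12.3% |

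The 16% row uses the placebo rate that section 1.1 cites from an earlier ITP trial ("the response rate overall was only 59% compared to 16% in placebo"). Its population and endpoint may differ.

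**3. What the regression returns.** For 20/40 vs 0/20, an ordinary fit gives a log odds ratio near 23.6 with standard error about 17,800 and Wald p = 0.999; Fisher p = 0.00004. For 12/24 vs 0/12, Wald p is again 0.999, against Fisher 0.0025 and likelihood-ratio 0.0004.

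| Table | Firth odds ratio (95%) | Exact conditional, median-unbiased (95%) | Difference (Miettinen-Nurminen 95%) |
|---|---|---|---|
| 20/40 vs 0/20 | 41.0 (5.0 to 5,342) | 26.2 (4.1 to infinity) | 50 points (31.6 to 64.9) |
| 12/24 vs 0/12 | 25.0 (2.7 to 3,333) | 14.8 (2.07 to infinity) | 50 points (21.9 to 68.8) |

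**4. Power and type I error.** All 2x2 tables were enumerated, and the binomial probabilities of those with p ≤ 0.05 summed. Wald counts zero-cell tables as non-significant. All figures are unadjusted and single-look.

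| Test | Power 50% vs 5%: N=60, N=36 | Highest type I error, null rates 5% to 40%: N=60, N=36 |
|---|---|---|
| Wald | 61.7%, 29.3% | not the issue here |
| Fisher | 97.6%, 81.5% | 3.7%, 2.9% |
| Firth | 98.2%, 86.7% | 5.1%, 4.5% |
| Score | 98.6%, 86.7% | 5.2%, 5.5% |
| Likelihood ratio | 98.8%, 91.5% | 7.4%, 6.8% |

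The Wald ceiling follows from step 2: it cannot exceed about 100 − 35.8 = 64.2% at N=60 or 100 − 54.0 = 46.0% at N=36. Over all null rates Firth reaches 5.5% at N=60.

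**5. Does the choice among usable tests matter?** Under 50% vs 5%, Fisher, Firth, score and likelihood ratio fail to agree in 1.2% of trials at N=60 and 10.1% at N=36. Including Wald, disagreement is 37.3% and 62.4%.

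**6. With a splenectomy term.** The documents give no split, so these are assumptions: 39/21 at N=60; 24/12 and 18/18 at N=36; 2:1 within stratum; equal response across strata. Firth power is 98.3% at N=60 and 86.9% at N=36, with type I error at most 5.5% and 4.7%.

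**The case against.** **The plan never says Wald.** This stands. A reader might infer that the plan prescribes a test with 62% or 29% power; it does not. Those figures apply only if Wald output is taken at face value in an empty-arm table. Likelihood-ratio and score p-values from the same model remain available, and at N=60 the usable tests almost always agree. What remains is that a switch made after seeing the empty arm is data-driven. That is hard to defend when subjects are unblinded one by one after Part 1 and an interim look has taken place.

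**Logistic regression may not be the intended primary test.** The sentence sits under an interim-analysis heading, covers CR and PR together and names no arm comparison, while 36 comes straight from a two-proportion formula. A two-proportion test is a plausible intention and would cope with an empty placebo arm. But no section names it, so the gap is the same.

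**Placebo response may be higher.** At 16% an empty arm is much rarer. Power at 50% vs 16%, N=60, is then Wald 72.6%, Fisher 71.0%, Firth 76.2% and likelihood ratio 77.8%. None reaches 80%, so that shortfall is mainly the smaller effect. At N=36 Wald still trails, at 36.1% against 51.6% for Firth.

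**Splenectomy.** A reader might infer that the stratum was left out of the model. The sentence lists no terms at all, not even treatment, so the terms are unspecified, not omitted. Adding splenectomy matches the randomisation but does not cure an empty arm.

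**Firth is a preference.** Fair: the score test does equally well on power and has a similar maximum error.

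**Conclusion.** This should be fixed. The one inferential analysis names a model but no test, terms or empty-arm rule, and at the plan's own inputs its ordinary odds ratio does not exist in 35.8% (N=60) or 54.0% (N=36) of trials.

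A reader might go further and infer that the trial cannot be tested or that the 80% power is wrong. Neither follows: usable tests exist, and the power reproduces at N=36 for two proportions. The defect is one of specification.

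The percentages assume an exact 2:1 split, the 5% placebo rate and a single look that ignores the analysis after 18 subjects. They apply to CR only, because the plan assumes no rate for PR.

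**What to change.** In 8.3.1.1, name one primary method that works with an empty arm, for example:

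> CR will be compared between randomised arms in the intention-to-treat population by Firth-penalised logistic regression with terms for treatment and splenectomy status (the randomisation stratum), with the penalised likelihood-ratio p-value and 95% profile interval. The difference in response proportions will be reported with a 95% Miettinen-Nurminen interval stratified by splenectomy status. The same methods apply if an arm has no responders, and to PR.

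A stratified score test or an exact test would also be acceptable as primary if named in advance. If exact conditional regression is used, report the median-unbiased estimate, because the conditional maximum-likelihood estimate is also infinite with an empty arm.

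**Cost.** Wording only; no added subjects or data. Firth shrinks the odds ratio, has a very wide upper limit in a zero-cell table and can slightly exceed 5% (up to about 5.5% at N=60). Relative to Firth, the unadjusted exact (Fisher) test gives up about 0.6 points of power at N=60 and 5 points at N=36 at 50% vs 5%, and about 5 points at either size at 50% vs 16%. In exchange it guarantees the level at a single look.

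Date the change and justify it from the design assumptions only, since an interim look has occurred and subjects are unblinded after Part 1. Do not carry the single-look power figures above into 8.2.1 as the design's power.
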